## **Objective 3:**

*Analysis* - Our primary unit of analysis for this implementation evaluation will be the VA-ADNA *institutional pairs* implementing this program. Thus, this will be a case-oriented analysis. Below we describe a three-stage team approach to analyze data, adapted from Damschroder and we will repeat these stages at each of the two data collection phases, ultimately integrating data at case-level to describe program implementation from two to eight months after randomization.

*Coding* - First, open-ended data from the interviews will be reviewed and coded by a team of two researchers. They will code transcribed data according to CFIR and ERIC constructs using directed content analysis, in which codes are developed *a priori*; additional data derived codes will be established for text that cannot be coded with the *a priori* codes. Thus, this will be primarily a deductive approach, and we will additionally create codes that are inductively derived from data. The researchers will first independently read through a subset of interviews (about three to five) to apply initial codes and then come together to compare codes and arrive at agreement through deliberation and consensus. The researchers will then develop a final list of codes and apply these codes to all responses.

Memos- Researchers will aggregate individual interviews from VA and ADNA key informants into case memos and identify whether CFIR constructs are manifested as facilitators or barriers and what implementation strategies are used. A case memo is a Word document in which quotes from individual interviews within each case are collated and organized by construct. To determine whether CFIR constructs manifest as facilitators or barriers, researchers will independently rate coded text according to strength and valence on a 5 point scale, with -2 reflecting a statement about a strong barrier to +2 reflecting a statement about a strong facilitator. They will again use a team approach to resolve differences through deliberation and discussion and arrive at final, agreed upon ratings. An overall rating for each construct will be established based on average of ratings for individual quotes under that construct. The memos will also include a summary statement to describe what was coded (e.g., how did key informants describe the innovation source) and whether implementation context or strategy can be ascribed to a specific entity (i.e., solely VA or ADNA) or if it is a shared strategy, and they will include a rationale for ratings (e.g., the program was mandated without buy-in from local entities, thus a strong negative rating). We will build on the case memos developed during the first data collection period with data from the second to describe implementation strategies and any updates from the first interview for cases that have two interviews.

Qualitative Comparative Analysis - The objective of this stage will be to consolidate collected implementation data to assess how combinations of strategies and barriers relate to outcomes using Qualitative Comparative Analysis (QCA). At the individual level, outcomes will be high report of unmet needs for personal care or very good to excellent satisfaction, analyzed as part of Objective1 and, for use in QCA, transformed to reflect presence or absence of these values. At the institutional level, outcomes will be the number of Veterans receiving care through VDHCBS as a proportion of the total number of Veterans receiving Home and Community Based Care one year after program start. QCA is a

quantitative, case-oriented method that uses applied set theory and Boolean algebra to examine multifactorial causality (i.e., when several variables together have a joint effect on an outcome). In essence, it offers a systematic way to compare cases for factors related to success of an outcome, distinguishing between necessary and sufficient conditions, in projects with small or medium-N. It is a well-established quantitative approach that has been in use since the 1980s, especially in political science, to answer research questions like "What combinations of conditions are directly connected to the outcome of interest, such that cases with those specific combinations also always had the outcome present?" Although quantitative, QCA is a form of case-oriented research that requires close familiarity with the gualitative dataset of interest and theoretical framework to interpret results. As Baptist and Befani say in their primer on QCA, "Put simply, QCA allows evaluators to answer the question 'what works best, why, and under what circumstances' quite literally, in a way that emerges directly from other empirical analysis; that can be replicated by other researchers, and is generalizable to other contexts." Because findings from QCA will be generalizable, even though we will be evaluating a subset of cases, they could be used to inform future expansion of VD-HCBS or assistance for struggling entities.

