As part of this objective, we will conduct individual interviews with VA and ADNA coordinators from 16 purposefully selected VA medical centers with recently established and existing VD-HCBS programs. The 32 coordinators will include 16 ADNA Coordinators and 16 VA coordinators from 16 VD-HCBS program sites. Whenever possible, each coordinator will be interviewed at two time points (64 total interviews). The first set of interviews with the coordinators, will be 2 to 4 months after GEC allows the program to begin enrolling Veterans (completion of the Lewin Group readiness review). The second set of interviews will be 6 months after the initial interview to obtain follow-up data about implementation process, compared to the initial startup time, implementation strategies that they have employed, and their evaluation of implementation success (See Interview Guides). If it is not possible to interview sites at 2months after GEC allowed to begin enrolling Veterans (completion of the Lewin Group readiness review), we will conduct one interview at least 6-months after readiness review. From the VA coordinators, we will request a local VAMC leader (n=16) and a VISN GEC leader (n=16) for one-time interviews (32 interviews). Additionally, we will ask the GEC VISN leads when we interview them to recommend local GEC contacts. Pair Interview Dropout. Our primary interest is in triangulating data from the VA and ADNA coordinators at a case level. However, there will be dropout and turnover in the coordinator positions. When there is dropout, we will seek to recruit another individual from the site to complete the pairwise analysis. If this is not possible, we will exclude that program site in the case-level analysis and continue to recruit until we have 16 program sites, with participation from both the VA and ADNA coordinators. We anticipate dropout of 25% in the pairwise analysis and are requesting permission to perform additional interviews at 4 sites (8 interviews)

Including the additional interviews to allow for the projected drop out rate, we estimate that a Total of 104 interviews will be conducted with a total of 72 individuals.

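### Averaging signed quote ratings over VA and ADNA informants can hide their disagreement: the construct rating falls near 0 or takes the sign of the more-quoted side

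*Combined protocol and SAP*

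**What the plan says.** The case is the VA-ADNA partnership. 7.0 Data Analysis, Objective 3, states: "Our primary unit of analysis for this implementation evaluation will be the VA-ADNA" institutional pair. 5.0 Study Procedures, Objective 3, gives the reason for interviewing both sides: "Our primary interest is in triangulating data from the VA and ADNA coordinators at a case level". A site that cannot supply both coordinators is left out of the case-level analysis and replaced.

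The memo paragraph of 7.0 then sets the rating rule:

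- Pooling: "Researchers will aggregate individual interviews from VA and ADNA key informants into case memos".
- Scale: five points, "with -2 reflecting a statement about a strong barrier to +2 reflecting a statement about a strong facilitator".
- Differences between raters: "They will again use a team approach to resolve differences through deliberation and discussion and arrive at final, agreed upon ratings". This settles differences between researchers, not between informants.
- Aggregation: "An overall rating for each construct will be established based on average of ratings for individual quotes under that construct".

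The purpose given for the ratings is to decide whether each CFIR construct acts as a facilitator or a barrier. The memo also keeps the quotes by construct, a summary statement, and a note of whether context or strategy belongs to VA, to ADNA or to both. Of the memos it adds that "they will include a rationale for ratings".

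The QCA paragraph that follows relates combinations of strategies and barriers to outcomes. It does not name the averaged rating as the QCA condition. It gives no cut-off and no treatment of values near 0.

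**The concern.** A mean of signed ratings offsets barriers against facilitators. It also weights each informant by the number of coded quotes. Both properties matter when the two halves of the pair see a construct differently, which is the situation the paired design exists to detect. Such differences are foreseeable: section 2.0 reports that an earlier evaluation found some VA-ADNA partnerships troubled, and the Objective 3 recruitment section selects sites partly on how well the partners collaborate.

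The imbalance in quotes need not come only from who talks more. The interview schedule itself has more VA-side than ADNA interviews per case once leaders are counted. At stake is whether the number that labels a construct as barrier or facilitator reflects both partners, in an analysis of 16 sites that is meant to inform further expansion.

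**Working it through.** The plan gives no numerical example of a construct rating, so there is no figure to reproduce. The check applies the stated rule to simple cases. All quote counts below are assumptions.

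**1. Formula.** Let one side give a quotes rated +2 and the other b quotes rated -2. The quote mean is (2a - 2b)/(a + b). Averaging within each side first and then weighting the sides equally gives (2 - 2)/2 = 0 for any a and b.

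| Quotes at +2 : quotes at -2 | Quote mean | SD of quotes | Equal-weight mean |
|---|---|---|---|
| 3 : 3 | 0.00 | 2.00 | 0 |
| 4 : 2 | +0.67 | 1.89 | 0 |
| 6 : 2 | +1.00 | 1.73 | 0 |
| 8 : 2 | +1.20 | 1.60 | 0 |
| 9 : 1 | +1.60 | 1.20 | 0 |
| 2 : 8 | -1.20 | 1.60 | 0 |
| all quotes rated 0 | 0.00 | 0.00 | 0 |

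The first and last rows have the same mean and opposite meanings. Only the spread separates them.

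**2. When the mean is near 0.** If s is the share of quotes at +2, the mean is 2s - 2(1 - s) = 4s - 2. It lies within ±0.5 only when s is between 0.375 and 0.625. Outside that band the rating takes the sign of the side with more quotes.

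**3. Interviews per case, from 5.0 Study Procedures, Objective 3.**

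- VA side: one coordinator interviewed twice, one local VAMC leader once, one VISN GEC leader once: 2 + 1 + 1 = 4.
- ADNA side: one coordinator interviewed twice: 2.

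The Objective 3 recruitment section lists these leaders among the interviews for each case, and the memo paragraph speaks of key informants, not of coordinators alone. Whether leaders' quotes enter the construct average is therefore likely but not stated.

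**4. Full disagreement with equal quotes per interview (VA side +2, ADNA -2).**

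- Two rounds, leaders included: (4×2 - 2×2)/6 = 4/6 = +0.67.
- One interview per coordinator, which the plan allows, leaders included: (3×2 - 1×2)/4 = +1.00.
- Coordinators only, two rounds: (2×2 - 2×2)/4 = 0.

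If the views are reversed, the signs reverse. In each case the two partners disagree as strongly as the scale permits, and the rating does not show it.

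**5. What equal weighting does.** It removes the dependence on quote counts, as the last column shows. It does not remove cancellation, because it returns 0 throughout. A separate rating per entity, or a flag for opposite signs, is needed for that.

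**The case against.** The strongest reply is that the number is not the whole record. The memo keeps the quotes, the attribution to VA or ADNA and the reasons for each rating, and the aggregation sentence speaks of a rating based on the average, which leaves some room for judgement. The QCA section also says that interpretation requires knowing the qualitative material closely. All of this stands. It limits the point to the numeric rating.

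Three stronger readings are tempting and are not supported:

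- A reader might infer that contested constructs enter the QCA as neutral. The plan never says that the mean is the QCA condition, and only near-balanced quotes average to about 0.
- A reader might infer that the partners' disagreement is erased. It remains in the memo text.
- A reader might infer that the average gives a wrong sign. That would treat equal VA and ADNA weight as the truth. The plan sets no such standard, and it expects some factors to belong to one partner alone. How often a construct is raised may also reflect its importance.

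Nor does a 0 equal a construct that nobody mentions: such a construct has no quotes and so no average.

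A further objection concerns the remedy. A third, mixed value does not fit well with Boolean QCA on 16 cases. This is correct, and the fix below uses a binary condition instead.

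What the objection does not answer is that the plan introduces the rating as the means of deciding between facilitator and barrier, gives no other rule for that decision, and states no safeguard for the case in which the partners differ.

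**Conclusion.** The point holds as a low-cost improvement to a stated rule, not as an error that invalidates Objective 3. Under disagreement, the averaged rating depends on the balance of quotes between the sides and does not show that they disagree. With leaders included, two rounds, equal quotes per interview and ratings of +2 against -2, the result is +0.67 towards the VA view; with one interview per coordinator it is +1.00; with coordinators only it is 0. These sizes rest on assumed quote counts and on the most extreme disagreement, and the plan gives no basis for saying how often it would occur. Because the step from rating to QCA condition is not specified, any effect on the QCA is a possibility only.

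**What to change.** In the memo paragraph of 7.0, Objective 3:

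1. Average quote ratings within each informant, then within each entity, to give a VA rating and an ADNA rating for each construct.
2. Report both beside any combined rating. If they are combined, weight the two entities equally.
3. Flag the construct as mixed when the two ratings have opposite signs.

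In the QCA paragraph, state before analysis how ratings become conditions. A mixed construct should not be treated as 0. It can be coded through a binary condition, such as whether either partner reports a barrier.

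The flag catches disagreement between entities. Opposing statements by the same informant, or by two informants on the VA side, can still offset each other within an entity's rating, so the memo text remains necessary.

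The cost is slightly more coding work on the same quotes with the same raters. The number of QCA conditions must also be kept small with 16 cases: four binary conditions already define 2^4 = 16 combinations, and five define 32.

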## 2.0 Introduction

In the next decade, the number of older high priority (P1a) Veterans will double. The VA has a statutory obligation to purchase or provide institutional care to all P1a Veterans. At a cost of \$110,000 per Veteran per year for institutional care, the ability of the VA system to honor its statutory obligations will be challenged with current resources. As stated by the 2013 Office of the Inspector General report,  there is a rapid need to rebalance the focus from institutional programs to non-institutional programs. In FY14, VA's Office of Geriatrics and Extended Care (GEC) spent 74% of its budget on institutional care and 26% on non-institutional long-term services and supports (LTSS). For comparison, state Medicaid programs, which are under a statutory obligation to provide institutional care, devote the majority (51%) of LTSS spending to non-institutional care. In an effort to meet this impending demand, GEC has been working toward developing a dynamic system of LTSS that shifts the delivery of long-term care (LTC) from institutions to the community.

As part of this rebalancing plan, GEC has implemented many innovative programs to postpone or prevent institutionalization. Recognizing the need to increase home and community-based services (HCBS) utilization for high-need Veterans and following the reported success of the Cash and Counseling Demonstration and Evaluation (CCDE), GEC leadership implemented a

program for Veterans to self-direct their care thereby enabling them to maintain community residence and avoid institutionalization: Veteran-Directed Home and Community Based Services (VD-HCBS). In 2008, a partnership was formed between VA and the Administration for Community Living (ACL) to implement the VD-HCBS program, capitalizing on the home care service delivery experience and skills of ACL's Aging and Disability Network Agencies (ADNAs) and the VHA's commitment and resources. Through this partnership, VAMCs purchase VD-HCBS care management from ADNAs on behalf of Veterans. GEC is planning an expansion of VD-HCBS to an additional 90 VA sites over the next 3 years.

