#### SIGNIFICANCE

**Knowledge to be gained.** Proponents of VD-HCBS suggest that expansion of this program could be one promising solution to meet the increased need for LTSS while containing costs and promoting Veteran-centered care. In addition, it provides an innovative approach to HCBS delivery to Veterans living in rural areas or far from VAMCs. Several VAMCs have documented the success of their programs both in terms of Veterans' satisfaction and reduced NH utilization,  However, uptake of the program varies greatly across the country: only 51 VAMCs offer VD-HCBS and the numbers of Veterans enrolled at each site range from one to 100+. There has been no formal evaluation of implementation or effectiveness of the program and therefore the evaluation we are proposing is significant because it will be the first major evaluation of the effect and implementation of the VD-HCBS program.

**Impact on Veterans and the VA.** Veterans enrolled in VD-HCBS represent a vulnerable population, with most having functional or cognitive deficits, needing >20 hours of home care, and meeting eligibility for long term care. At a cost of \$110,000 per Veteran per year for long-

Version 04/23/2018

term care and a doubling of the number of Veterans eligible for VA-paid long-term care, GECs and Veterans have a mutual interest in preserving Veteran independence in the community. As a result, VD-HCBS has tremendous opportunity to improve the fiscal outlook of GEC's LTSS while delivering the highest level of Veteran-centered care. This proposed VD-HCBS evaluation leverages the utilization analysis of PEPReC, by systematically capturing perspectives of Veterans and Caregivers to provide a comprehensive view of the value of VD-HCBS to all stakeholders.

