## Recruitment Methods:

All quantitative data will be obtained from the data owners (VHA Office of GEC), following an approved Data Use Agreement in accordance with VHA policy. As

part of standard operations, the ADNA meets with the Veteran initially and every 90 days thereafter. During these meetings it is customary for the ADNA to ask about current services, as well as, unmet needs and satisfaction with the program.

The VD-HCBS program currently enrolls ~825 new Veterans annually at existing sites. At newly opened sites, there is a period between readiness review and enrolling Veterans that delays early recruitment. As a result, we anticipate that ~825 Veterans among the new sites will be enrolled annually. With 4 routine ADNA assessments per Veteran, we expect to receive up to 6,600 surveys.

A total of 64 respondents consisting of Veterans or Caregivers will be recruited for qualitative portion of this objective. Recruitment packets will initially be sent using via US Mail to the Veterans' listed residences in the ADNA assessment data or should the addresses not be listed, by using the listed SSN in the ADNA assessment data to access the national Electronic Health Record (EHR) by way of CAPRI/VistAWeb and/or JLV. We will randomly select four Veterans enrolled in VD-HCBS from each of the 16 VAMCs chosen for the implementation analysis described in Objective 3. Veteran selection will be done by inputting all case numbers at a VAMC into a random number generator. This packet will include an introduction letter, refusal postcard, and the CIRB approved information consent sheet. The letter will inform potential participants about the interview, the goal of the interviews, that the interviews will be recorded for transcription purposes and will provide contact information for a Providence-based project staff member to address any questions or concerns they may have prior to participating. They may also use this telephone number to indicate their refusal to participate.

The CIRB approved information consent sheet for Veterans to keep, will describe the procedures and risks and contain contact information should they have any questions.

Also included will be the refusal to participate postcard. Veterans will be asked to complete and return this postcard if they do not wish to participate in the study. Receipt of this postcard by the project staff will terminate all future contact with the Veteran regarding this project.

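### The QCA codes each site's Veteran outcome as present or absent with no allowance for sampling error, although mean intake is only about 9 to 16 new Veterans per site a year

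*Combined protocol and SAP*

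**What the plan says.** Section 7.0, Objective 3, sets the unit: "Our primary unit of analysis for this implementation evaluation will be the VA-ADNA" institutional pair. Section 5.0, Objective 3, says there will be "16 purposefully selected VA medical centers with recently established and existing VD-HCBS programs".

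The QCA paragraph in section 7.0 names two kinds of outcome. The institutional one is the share of Home and Community Based Care Veterans who receive VD-HCBS one year after program start. The individual-level ones are high unmet need for personal care, or very good to excellent satisfaction. These come from Objective 1 and are, "for use in QCA, transformed to reflect presence or absence of these values". For the individual-level outcomes the section does not say how many Veterans' answers become one site value, at what cut-off, at what time point, or with how few Veterans. It has no sensitivity analysis. It illustrates QCA with a question about combinations whose cases always show the outcome, and it describes the findings as generalizable and usable for future expansion.

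On numbers, section 5.0 (Objective 1, Recruitment Methods) says: "The VD-HCBS program currently enrolls ~825 new Veterans annually at existing sites". For new sites, "we anticipate that ~825 Veterans among the new sites will be enrolled annually". The Significance section reports that "only 51 VAMCs offer VD-HCBS and the numbers of Veterans enrolled at each site range from one to 100" or more. The Introduction says "GEC is planning an expansion of VD-HCBS to an additional 90 VA sites over the next 3 years".

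**The concern.** Because the case is a site pair, the answers of many Veterans have to become a single present/absent value per site. If a site contributes 9 or 16 Veterans, its observed proportion can easily fall on the other side of the cut-off from its underlying proportion. Present/absent coding then gives that site the same certainty as one with 100 Veterans. This is error in the outcome itself, distinct from differences in case mix and from configurations that arise by chance among few cases.

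QCA is sensitive to such error. One miscoded site can make a sufficient combination of strategies look inconsistent, or let a spurious one look consistent. What is at stake is the Veteran-level part of Objective 3c, and the claim that its configurations can guide expansion or help struggling sites.

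**Working it through.** **1. The plan's own figure.** "With 4 routine ADNA assessments per Veteran, we expect to receive up to 6,600 surveys". Check: (825 + 825) × 4 = 6,600. It reproduces, so the enrolment inputs are being read as the plan intends.

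**2. Veterans per site per year.** Existing sites: 825/51 = 16.2. New sites, all 90 open: 825/90 = 9.2. If only 30 new sites were open (an assumption), 825/30 = 27.5. Three years at an existing site: 3 × 16.2 ≈ 48.

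**3. One site near the cut-off.** Suppose the cut-off is 70% (an assumption). A site with 9 Veterans needs 7 positive answers to be coded present; one with 16 needs 12. If the true proportion is 0.75, binomial probabilities give a present code with probability 0.60 (n = 9) or 0.63 (n = 16), so the code is wrong 40% or 37% of the time. At a true 0.90 it is wrong 5% or 2% of the time. The problem is therefore concentrated near the cut-off.

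**4. All sites.** The documents give no prevalence, between-site spread or cut-off, so these are assumed and varied. True site proportion ~ Beta with mean m and SD s; observed count ~ Binomial(n, p). A site is miscoded when its true and observed proportions lie on opposite sides of the cut-off. Percentage of sites miscoded, m = 0.70:

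| Cut-off | s | n = 9 | n = 16 | n = 48 |
|---|---|---|---|---|
| 0.70 | 0.05 | 39.7 | 36.8 | 29.2 |
| 0.70 | 0.10 | 30.8 | 26.5 | 17.9 |
| 0.70 | 0.15 | 23.6 | 19.4 | 12.0 |
| 0.70 | 0.20 | 18.0 | 14.3 | 8.6 |
| 0.50 | 0.05 | 11.0 | 3.7 | 0.8 |
| 0.50 | 0.10 | 13.2 | 7.1 | 3.9 |
| 0.50 | 0.15 | 13.7 | 9.0 | 5.6 |
| 0.50 | 0.20 | 12.4 | 9.0 | 5.5 |

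With the cut-off at the mean and m from 0.5 to 0.8, the full range for n = 9 or 16 is 11.2% to 40.4%. With m = 0.8 and a cut-off of 0.5 it is 0.5% to 7.1%.

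**5. Cross-check.** For a cut-off at the mean, the normal approximation is arccos(√R)/π, with R = s² / [s² + (m(1−m) − s²)/n]. For m = 0.70, s = 0.10, n = 9: R = 0.01/(0.01 + 0.20/9) = 0.310, giving 31.2% against 30.8% simulated. For n = 16: R = 0.01/(0.01 + 0.20/16) = 0.444, giving 26.8% against 26.5%.

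**6. Unequal site sizes.** Drawing n from a lognormal clipped to 1-120 (an assumption), with m = 0.70, s = 0.10 and the cut-off at the mean, gives 33.1% at a mean intake of 9.2 and 29.6% at 16.2.

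**7. Effect over 16 cases.** Treating sites as independent, the chance that all 16 codes are right is (1 − r)^16: 0.89^16 = 0.15 at r = 11%, and 0.75^16 = 0.01 at r = 25%.

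**The case against.** **The intake figures are rough.** 825/90 supposes all 90 new sites are open at once, whereas the expansion is spread over three years. Both figures are means for one year, and the Gantt chart shows Veteran survey analysis running from FY17 Q2 to FY20 Q1, so Veterans can accumulate. The range from one to more than 100 refers to Veterans enrolled, not yearly intake. Objective 1b draws four Veterans from each of the same 16 centers, so a one-Veteran site is unlikely to be among them. All this stands. It lowers the miscoding rate but does not remove it: about 48 Veterans per site still leaves 12-18% in the middle scenarios with the cut-off at the mean.

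**The cut-off may lie away from the mean.** Then the rate is mostly below 15%. That also stands, but the plan names no cut-off, and one far from the mean would leave few sites on one side and so little contrast for a QCA.

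**The assessments are close to a census.** They are given to every Veteran at the initial visit and quarterly thereafter, so a site's observed proportion could be taken as its outcome, without sampling error. That would be fair if the QCA only described these Veterans at these sites. Section 7.0 goes further and calls the findings generalizable, which makes the site's underlying proportion the relevant target.

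**Stronger readings.** A reader might infer that a quarter to a third of the 16 sites will be miscoded. That fits only particular scenarios, such as one year of data, a between-site SD near 0.10 and a cut-off at the mean; none of these is in the documents. A reader might also infer that the plan cuts a single assessment wave or applies a fixed consistency threshold. It states neither. That it treats the code as free of error is an inference from its silence.

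**Conclusion.** The concern holds in limited form. The plan reduces the Veteran outcome to one present/absent code per site, allows nothing for sampling error, and calls the resulting configurations generalizable. At a mean of about 9 to 16 new Veterans per site a year, codes for sites near the cut-off are unreliable.

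The size can only be given as a range under assumptions. On one year's intake with the cut-off at the mean, about 11-40% of sites are miscoded (between-site SD 0.05-0.20, mean 0.5-0.8), which is 1.8 to 6.4 of 16. With a cut-off well away from the mean it is mostly below 15%. With 48 Veterans per site it is about 12-18%, or 1.9 to 2.9 of 16 (mean 0.70, SD 0.10-0.15, cut-off at the mean).

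It would go too far to conclude that Objective 3c as a whole cannot link strategies to outcomes. The institutional outcome, the VD-HCBS share, does not depend on survey answers and is untouched. For the Veteran-level outcome, the documents support a warning about stability, not a finding that the analysis must fail.

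**What to change.** In section 7.0, Objective 3, for the Veteran-level outcome:

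- State in advance how Veterans' answers become one site value and at what cut-off. Form that value from all Veterans and all enrolment years available in the ADNA data.
- Repeat the QCA over bootstrap resamples of Veterans within sites, or with sites near the cut-off relabelled. Resample Veterans rather than assessments, since repeated assessments of one Veteran are correlated. For a site with very few Veterans use relabelling: resampling a single Veteran always returns the same answer and would look falsely stable.
- Report beside each configuration the share of resamples in which it survives.
- Limit the generalizability claim for this outcome to configurations that are stable.

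A multilevel model alone would not be enough. With the cut-off at the overall mean, a simple random-intercept estimate shrinks a site toward the mean but not across it, so no code changes. Dropping ambiguous sites, or publishing only configurations that survive, is also a trade-off: the first shrinks a 16-case analysis, and the second can discard true configurations with spurious ones. Reporting stability avoids both.

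The cost is a little more analysis of data already to be obtained, with no new collection. Fewer configurations may be claimed as generalizable.
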